11.1.3 Severity Criteria (Grade 1-5)

Definitions found in the CTCAE v4.03 will be used for grading the severity (intensity) of AEs. The CTCAE v4.03 displays Grades 1 through 5 with unique clinical descriptions of severity for each referenced AE. Should a subject experience any AE not listed in the CTCAE v4.03, the following grading system should be used to assess severity:

- Grade 1 (Mild AE) experiences which are usually transient, requiring no special treatment, and not interfering with the subject's daily activities
- Grade 2 (Moderate AE) experiences which introduce some level of inconvenience or concern to the subject, and which may interfere with daily activities, but are usually ameliorated by simple therapeutic measures
- Grade 3 (Severe AE) experiences which are unacceptable or intolerable, significantly interrupt the subject's usual daily activity, and require systemic drug therapy or other treatment
- Grade 4 (Life-threatening or disabling AE) experiences which cause the subject to be in imminent danger of death
- Grade 5 (Death related to AE) experiences which result in subject death

11.1.4 Causality (Attribution)

The Investigator is to assess the causal relation (ie, whether there is a reasonable possibility that the study drug caused the event) using the following definitions:

Not Related:	Another cause of the AE is more plausible; a temporal sequence cannot be established with the onset of the AE and administration of the investigational product; or, a causal relationship is considered biologically implausible.
Unlikely:	The current knowledge or information about the AE indicates that a relationship to the investigational product is unlikely.
Possibly Related:	There is a clinically plausible time sequence between onset of the AE and administration of the investigational product, but the AE could also be attributed to concurrent or underlying disease, or the use of other drugs or procedures. Possibly related should be used when the investigational product is one of several biologically plausible AE causes.
Related:	The AE is clearly related to use of the investigational product.

11.2 Unexpected Adverse Events

An "unexpected" AE is an AE that is not listed in the Investigator's Brochure/package insert or is not listed at the specificity or severity that has been observed. For example, hepatic necrosis would be "unexpected" (by virtue of greater severity) if the Investigator's Brochure referred only to elevated hepatic enzymes or hepatitis. Similarly, cerebral thromboembolism and cerebral vasculitis would be "unexpected" (by virtue of greater specificity) if the Investigator's Brochure/package insert listed only cerebral vascular accidents. "Unexpected" also refers to AEs that are mentioned in the Investigator's Brochure as occurring with a class of drugs or as anticipated from the pharmacological properties of the drug, but are not specifically mentioned as occurring with the study drug under investigation.

11.3 Special Reporting Situations

Special reporting situations on a Sponsor study that may require expedited reporting and/or safety evaluation include, but are not limited to:

- Overdose of any study drug
- Suspected abuse/misuse of a study drug
- Inadvertent or accidental exposure to a study drug
- Medication error involving a product (with or without subject exposure to the study drug, eg, name confusion)

Occurrence of any special reporting situations should be recorded in the eCRF. If any special reporting situation meets the criteria of an AE, it should be recorded on the AEs eCRF. If the AE is considered serious, it should be recorded on the AEs eCRF as serious and should be reported on the Serious Adverse Event Report Form. The SAE Report Form should be sent via email or fax to Pharmacyclics Drug Safety or designee within 24 hours of awareness.

11.4 Documenting and Reporting of Adverse Events and Serious Adverse Events by Investigators

11.4.1 Assessment of Adverse Events

Investigators will assess the occurrence of AEs and SAEs at all subject evaluation time points during the study. All AEs and SAEs whether volunteered by the subject, discovered by study personnel during questioning, detected through physical examination, clinically significant laboratory test, or other means, will be recorded in the subject's medical record and on the Adverse Event CRF and, when applicable, on the Serious Adverse Event Report Form.

Each recorded AE or SAE will be described by its duration (ie, start and end dates), severity, regulatory seriousness criteria (if applicable), suspected relationship to the investigational product, and any actions taken.

11.4.2 Adverse Event Reporting Period

All AEs, whether serious or non-serious, will be documented in the source documents from the time the signed and dated ICF is obtained until 30 days following the last dose of ibrutinib and 90 days following the last dose of MEDI4736. SAEs will be reported to the Sponsor from the time of ICF signing. Non-serious AEs will be recorded in the eCRF from the first dose of study drug until 30 days after the last dose of ibrutinib and 90 days following the last dose of MEDI4736. If both study drugs were discontinued at the same time, an SAE after 30 days and up to 90 days from the last dose of study drugs should indicate the causality for MEDI4736 only and N/A for ibrutinib (unless there is a causal relationship to ibrutinib).

SAEs reported after 30 days following the last dose of ibrutinib and 90 days following the last dose of MEDI4736 should also be reported if considered related to study drug. Resolution information after 30 days following the last dose of ibrutinib and 90 days following the last dose of MEDI4736 should be provided.

Subjects who discontinued investigational product for unacceptable AEs will be followed until there is a return to the subject's baseline condition, or until the Investigator considers that a clinically satisfactory resolution is achieved. Subjects will also be contacted to document any new onset AEs and follow any AEs that were ongoing at the time of investigational product discontinuation.

Progressive disease should NOT be reported as an event term, but instead symptoms/clinical signs of disease progression may be reported (see Section 11.1.1).

All AEs, regardless of seriousness, severity, or presumed relationship to study drug, must be recorded using medical terminology in the source document. All records will need to capture the details of the duration and the severity of each episode, the action taken with respect to the study drug, the Investigator's evaluation of its relationship to the study drug, and the event outcome. Whenever possible, diagnoses should be given when signs and symptoms are due to a common etiology (eg, cough, runny nose, sneezing, sore throat, and head congestion should be reported as "upper respiratory infection"). Investigators must record in the CRF their opinion concerning the relationship of the adverse event to study therapy. All measures required for adverse event management must be recorded in the source document and reported according to Sponsor instructions.

All deaths should be reported with the primary cause of death as the AE term, as death is typically the outcome of the event, not the event itself. Autopsy and postmortem reports must be forwarded to the Sponsor, or designee, as outlined above, if allowed per local regulatory guidelines.

If a death occurs within 30 days after the last dose of ibrutinib or 90 days after the last dose of MEDI4736, the death must be reported to the Sponsor as an SAE.

11.4.3 Expediting Reporting Requirements for Serious Adverse Events

All SAEs (initial and follow-up information) will be reported on the Serious Adverse Event Report Form and sent via email or fax to Pharmacyclics Drug Safety, or designee, within 24 hours of the discovery of the event or information. Pharmacyclics may request follow-up and other additional information from the Investigator (eg, hospital admission/discharge notes and laboratory results). The contact information (phone, email and fax) for Pharmacyclics Drug Safety can be found on the Serious Adverse Event Report Form and instructions. All SAEs that have not resolved by the end of the study, or that have not resolved upon discontinuation of the subject's participation in the study, must be followed until any of the following occurs:

- The event resolves
- The event stabilizes
- The event returns to baseline, if a baseline value/status is available
- The event can be attributed to agents other than the study drug or to factors unrelated to study conduct
- It becomes unlikely that any additional information can be obtained (subject or health care practitioner refusal to provide additional information, lost to follow-up after demonstration of due diligence with follow-up efforts)

The Sponsor assumes responsibility for appropriate reporting of AEs to the regulatory authorities and governing bodies according to local regulations.

The Investigator (or Sponsor where required) must report these events to the appropriate Independent Ethics Committee/Institutional Review Board (IEC/IRB) that approved the protocol unless otherwise required and documented by the IEC/IRB.

11.4.4 Pregnancy

Before study enrollment, subjects must agree to take appropriate measures to avoid pregnancy. However, should a pregnancy occur in a female study subject, consent to provide follow-up information regarding the outcome of the pregnancy and the health of the infant until 30 days old will be requested.

A female subject must immediately inform the Investigator if she becomes pregnant from the time of consent to 90 days after the last dose of study drug. A male subject must immediately inform the Investigator if his partner becomes pregnant from the time of consent to 90 days after the last dose of study drug. Any female subjects receiving study drug(s) who become pregnant must immediately discontinue study drug. The Investigator should counsel the subject, discussing any risks of continuing the pregnancy and any possible effects on the fetus.

Although pregnancy itself is not regarded as an AE, the outcome will need to be documented. Any pregnancy occurring in a subject or subject's partner from the time of consent to 90 days after the last dose of study drug. Any occurrence of pregnancy must be recorded on the Pregnancy Report Form Part I and sent via email or fax to Pharmacyclics Drug Safety, or designee, within 24 hours of learning of the event. All pregnancies will be followed for outcome, which is defined as elective termination of the pregnancy, miscarriage, or delivery of the fetus. For pregnancies with an outcome of live birth, the newborn infant will be followed until 30 days old by completing the Pregnancy Report Form Part II. Any congenital anomaly/birth defect noted in the infant must be reported as an SAE.

11.4.5 Other Malignancies

All new malignant tumors including solid tumors, skin malignancies and hematologic malignancies will be reported for the duration of study treatment and during any protocol-specified follow-up periods including post-progression follow-up for overall survival. Other malignancies will only be reported as an SAE if the event meets any serious adverse event reporting requirement listed under section "Serious Adverse Event" (otherwise captured as an AE in the eCRF).

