1.3.4.6. Other Malignancies

Other malignancies, most frequently skin cancers, have occurred in subjects treated with ibrutinib. Across the MCL (PCYC-1104-CA) and CLL/SLL studies (PCYC-1112-CA and PCYC-1102-CA), non-melanoma skin cancers and non-skin cancers were reported in 5.0% (18/357) and 2.5% (9/357) of subjects who received ibrutinib, respectively.

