8.3.4 Survival Follow-up

Once subjects progress or start use of alternative anticancer therapy (for subjects who have not withdrawn consent), they will be contacted approximately every 12 weeks (\pm 7 days) from the last dose by clinic visit or telephone to assess survival and the use of alternative anticancer therapy, up to 3 years after the last dose of the last subject enrolled. Subjects will be contacted until death, subject withdrawal, lost to follow-up, or study termination by the Sponsor, whichever occurs first.

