4.2. Safety Analyses

Safety data will be summarized by tumor type cohorts. Table 2 summarizes the safety analyses to be performed for all tumor type cohorts.

Adverse events (AEs) will be coded in accordance with the Medical Dictionary for Regulatory Activities (MedDRA). Severity of AEs will be graded by the investigator according the NCI-CTCAE v4.03.

All laboratory values will be converted to and reported as international standard (SI) units. In general, only data from the central laboratory will be summarized and analyzed. Laboratory parameters will be graded using the NCI CTCAE v4.03.

Unless otherwise specified, only baseline and post-baseline values collected during the treatment-emergent period will be included in the safety analysis. A treatment-emergent adverse event is defined as any event that begins or worsens in either intensity or frequency on or after the first dose of study treatment (either ibrutinib or MEDI4736). Only treatment-emergent adverse events (TEAEs) occurring and reported during the study period will be included in the adverse event summaries. The TEAEs will be derived as those events that 1) occur after the first dose of study drug (either ibrutinib or MEDI4736), through the 30 days following the last dose of ibrutinib or 90 days following the last dose of MEDI4736 (whichever date is later); 2) any event with missing onset date and its resolution date during the treatment phase; 3) any event that is considered study drug-related regardless of the start date of the event; or 4) any event that is present at baseline but worsens in severity, seriousness, or becomes subsequently considered drug-related by the investigator.

Table 2: Summary of Safety Analyses

Safety Assessment	Definition	Analysis Methods
Safety and tolerability	
AE: TEAEs, SAEs, grade 3 or worse TEAEs, related TEAEs, TEAEs leading to treatment discontinuation, TEAEs leading to dose reduction, TEAEs leading to death, protocol- defined events of special interest, and other safety observations
 
Worst post-baseline toxicity grade for selected lab tests: Worst post-baseline toxicity grade, Hgb, creatinine clearance, abnormal uric acid, liver function abnormalities
 
Vital signs (blood pressure, heart rate, temperature, respiratory rate), and weight
	Descriptive summary statistics and/or listings

AE: adverse event; SAE: serious adverse event; TEAE: treatment-emergent adverse event

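### New malignancies must be reported through survival follow-up, but the 30/90-day adverse-event window, the survival contact and the SAP's treatment-emergent rule make no provision for late ones, so this named ibrutinib risk may be under-counted.

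*Protocol*

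**What the plan says.** **The duty.** Protocol Section 11.4.5 says that new malignant tumors of all kinds must be reported on treatment and also "during any protocol-specified follow-up periods including post-progression follow-up for overall survival". Those that meet a seriousness criterion go in as SAEs; the rest are "otherwise captured as an AE in the eCRF".

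**The recording window.** Section 11.4.2 says "Non-serious AEs will be recorded in the eCRF from the first dose of study drug until 30 days after the last dose of ibrutinib". For MEDI4736 the limit is 90 days from its last dose. SAEs after that point "should also be reported if considered related to study drug". Section 7.1.1.5 gives the same 30- and 90-day limits and adds initiation of alternative cancer therapy as a stopping point. The adverse-event row of Appendix 1 ends at 30 and 90 days. None of these exempts malignancies.

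**The follow-up contacts.** Response follow-up (8.3.3) lists physical examination, CT or MRI, PET if needed, and response assessment. Survival follow-up (8.3.4), by visit or telephone about every 12 weeks, is there "to assess survival and the use of alternative anticancer therapy". The Survival FU column of Appendix 1 matches that.

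**The analysis.** SAP Section 4.2 states: "Only treatment-emergent adverse events (TEAEs) occurring and reported during the study period will be included in the adverse event summaries". The derivation closes at the later of 30 days after ibrutinib and 90 days after MEDI4736, except for drug-related events and baseline events that worsen or are later judged related.

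**The risk.** Section 1.3.4.6 names other malignancies as an ibrutinib risk. In the MCL and CLL/SLL studies it cites, they "were reported in 5.0% (18/357) and 2.5% (9/357) of subjects who received ibrutinib"; the first figure is for non-melanoma skin tumors and the second for tumors outside the skin.

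**The concern.** A site that follows Sections 7.1.1.5 and 11.4.2 and Appendix 1 to the letter would not meet Section 11.4.5. For a non-serious tumor found after the window, one section says to enter it in the eCRF and another says entry has closed. For a serious tumor judged unrelated, one section says to report it and another asks only for related events. The stop at alternative cancer therapy bears hardest on post-progression subjects, whom 11.4.5 expressly includes.

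Safety and tolerability is a primary objective in Phase 1b and a secondary one in Phase 2. If late malignancies are collected unevenly and then have no planned output, readers of the report could take the treatment-emergent count for the whole-study count that 11.4.5 implies. With only a few cases expected, one or two missing would change the reported rate noticeably.

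**Working it through.** **1. The plan's own figures.** From Section 1.3.4.6: 18/357 = 5.04% and 9/357 = 2.52%, agreeing with the stated 5.0% and 2.5%. Exact (Clopper-Pearson) 95% intervals are 3.0% to 7.9% and 1.2% to 4.7%.

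**2. One case traced through the text.** Take a new, non-serious skin cancer found in survival follow-up, after the window, and judged unrelated.
- 11.4.5: must be reported, as an AE in the eCRF.
- 7.1.1.5, 11.4.2 and the Appendix 1 AE row: recording has closed.
- 8.3.4 and the Survival FU column: no prompt for it.
- SAP 4.2 derivation: onset is after the window; the onset date is not missing; the event is not drug-related; it was not present at baseline. It meets none of the four routes. The opening sentence of the SAP definition has no end date, but the derivation that follows it does.
- Section 11.4.6 and SAP Table 2: the events of special interest are major hemorrhage, pneumonitis, hypersensitivity and hepatic abnormalities, so that line of Table 2 does not pick it up.
- SAP Section 5: no change to malignancy reporting is listed.

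**3. Follow-up time outside the window.** Inputs: 30 and 90 days (11.4.2); follow-up of T years after last dose, an assumption because it varies by subject. Share inside = window / (365.25 × T).

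| T (years) | 30-day window | 90-day window |
|---|---|---|
| 1 | 8.2% | 24.6% |
| 3 | 2.7% | 8.2% |
| 5 | 1.6% | 4.9% |

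At T = 3, about 92% (1 − 90/1096) to 97% (1 − 30/1096) of post-treatment time lies under the 11.4.5 duty but outside the window. This is a share of time, not of events.

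**4. Expected total cases.** Formula: N × 18/357 and N × 9/357. With N = 73 (Phase 2): 3.7 and 1.8. With N = 109 (Section 10.4): 5.5 and 2.7; 109 may count Phase 1b subjects at the recommended dose twice, since they also count toward Phase 2. Both assume that rates and follow-up from MCL and CLL/SLL studies carry over to FL and DLBCL.

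**5. What would reach the summaries.** Let f be the share of cases that arise after the window and are not called related. The documents give no value for f, so this is only a range. Cases left = expected × (1 − f), with N = 73:

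| f | Non-melanoma skin | Non-skin |
|---|---|---|
| 0 | 3.7 | 1.8 |
| 10% | 3.3 | 1.7 |
| 25% | 2.8 | 1.4 |
| 50% | 1.8 | 0.9 |
| 75% | 0.9 | 0.5 |

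**The case against.** The best defense is that the protocol has other routes to these events.

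- Section 11.4.1 tells investigators to assess AEs at every subject evaluation, which can fairly be read to include response follow-up visits. Those visits also include an examination and neck-to-pelvis CT. This stands for response visits; it is less clear for a survival telephone call.
- The End-of-Treatment visits (8.3.1, 8.3.2) belong to the follow-up phase and review AEs. A reader might infer that no follow-up visit asks about malignancies at all; these visits show otherwise. They fall at 30 and 90 days, however, which is the edge of the window.
- Section 11.4.2 says subjects will be contacted about new-onset AEs. It gives no schedule or end date, follows a sentence about subjects who stopped for unacceptable AEs, and has no row in Appendix 1.
- Survival contacts record later anticancer therapy, which could reveal a systemically treated second cancer. CRF completion guidelines (12.7) are separate and not available here, so they may contain a prompt.
- SAP Table 2 has an open category for other safety observations and allows listings. Nothing forbids a listing of late malignancies, and reported events stay in the database. But nothing commits to one either.
- A treatment-emergent rate is not wrong for being limited to its period, and no malignancy rate is a planned endpoint. ORR and the dose decision are unaffected.

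These points limit the reach of the concern. They do not reconcile 11.4.5 with the recording window, and they supply neither a prompt in the survival contact nor a committed output.

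**Conclusion.** The point holds as a conflict between sections with a possible, unquantified loss of safety information. Section 11.4.5 sets a duty that the recording window contradicts, the survival contact does not prompt for, and the SAP does not commit to report when the event is late and judged unrelated.

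Three stronger readings should be avoided. First, that malignancies will certainly be under-counted: 11.4.5 itself obliges sites to report, so only a risk of under-counting is shown. Second, that 3.7 and 1.8 are missed cases: they are expected totals, resting on rates from other diseases and on similar follow-up, and the number lost depends on f, which the documents do not give. Third, that second cancers on ibrutinib appear late: Section 1.3.4.6 gives counts and no timing. The time shares in the working vary by subject as well. Section 5.5 allows ibrutinib for up to 3 years, and a subject treated that long is inside the window throughout treatment.

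**What to change.** 1. In Protocol 7.1.1.5, 11.4.2 and the Appendix 1 AE row, exempt new malignancies from the 30- and 90-day limits and from the stop at alternative cancer therapy, and state that late serious malignancies are reported regardless of causality. Without this step, added questions would leave sites with conflicting recording instructions.
2. Add a new-malignancy item to 8.3.3, to 8.3.4, and to the Response FU and Survival FU columns of Appendix 1.
3. In SAP 4.2 and Table 2, add one summary or listing of all other malignancies from first dose to end of follow-up, regardless of treatment-emergent status or causality. Separate non-melanoma skin from other cancers so that it can be read against Section 1.3.4.6, and show subsequent anticancer therapy and person-time.

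The cost is one question at a contact already made about every 12 weeks, an eCRF page kept open, and one extra output. The reported rate may be higher and will include some events that follow later therapies, which is why the output should show those therapies.

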11.4.6 Adverse Events of Special Interest (AESI)

Specific AEs, or groups of AEs, will be followed as part of standard safety monitoring activities by the Sponsor. These events (regardless of seriousness) should be reported on the Serious Adverse Event Report Form and sent via email or fax to Pharmacyclics Drug Safety, or designee, within 24 hours of awareness.

